CBZ may interact with other anticonvulsants, including half-life shortening when given with phenobarbital, phenytoin and primidone and half-life prolongation with valproate. Several drugs inhibit the elimination of CBZ and therefore elevate its serum levels, including erythromycin, isoniazid, triacetyloleandomycin, destropoxyphene, viloxazine, nicotinamide, verapamil and diltiazem. CBZ itself can affect the serum concentrations of other drugs, including valproate, ethosuximide, doxycycline, clonazepam, haloperidol, phenytoin and warfarin.

These drug interactions may necessitate changes in dose of CBZ or other drugs but do not prohibit the use of CBZ or other drugs while administering CBZ. These changes will be directed by the Sponsor-Investigator or sub-investigators.

ADVERSE EVENTS AND TOXICITY MANAGEMENT

Subjects will be closely monitored for the major side effects of CBZ, including allergic reaction, sedation, and bone marrow depression as well as for hepatotoxicity that could worsen the liver disease. This will include history, clinical examination and laboratory testing. Monitoring will be carried out at each study visit. In general it will not be necessary to reduce the dose of CBZ or discontinue CBZ unless there is an obvious allergic reaction, progressive hematological toxicity that includes aplastic anemia, neutropenia and/or thrombocytopenia, progressive hepatic toxicity with rising transaminases, decreasing albumin levels or prolongation of the prothrombin time, unremitting sedative effect, or CBZ levels in the toxic range.

In the event that a subject temporarily discontinues drug for any reason OR an investigator determines the a subject should temporarily hold study drug due to a clinical reason, we will reinitiate therapy based upon the following parameters;

A Preliminary Study of the Efficacy and Safety of Carbamazepine in Severe Liver Disease Due to Alpha-1 Antitrypsin Deficiency

-If study drug has been stopped for less than or equal to 5 days the subject will resume taking the previous dose.

[figure not shown]
-If study drug has been stopped for more than 5 days but less than or equal to two weeks, the subject will resume half of the previously assigned dose (if half the previous dose is unavailable, the next available formulation close to but less than half the previous dose is acceptable) for one week and return to the full previous dose 7 days later.

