CBZ and its metabolites are transferred to breast milk and can result in transient cholestatic hepatitis[45]. The estimated dose given to a breast feeding infant is 2-5 mg/kg/day. Breast feeding will not be allowed while the mother is receiving CBZ.

Adverse events

Definition

An adverse event (AEs) is any adverse change from the patient's baseline (pre-treatment) condition, including intercurrent illness which occurs during the course of the trial, after the consent form has been signed, whether the event is considered related to treatment or not.

A serious adverse event (SAE) is an untoward medical occurrence that results in any of the following: Death, or an event that is either life-threatening (risk of death at the time of the event) requires in-patient hospitalization or prolongation of existing hospitalization, or results in persistent or significant disability/incapacity or congenital abnormality or birth defect. Important medical events that do not result in one of the events listed above may be considered a serious adverse event when, based upon appropriate medical judgment, they may jeopardize the patient and may require medical or surgical intervention to prevent one of the outcomes listed above.

A SAE which is unexpected and is drug related (even remotely) will require expedited reporting to the FDA and the University of Pittsburgh IRB in accordance with respective timeline requirements. The following events are disease outcomes and will not be considered to be serious adverse events as they can occur in the usual course of patients with AT deficiency.

1. Development of hepatocellular carcinoma
2. Complications associated with chronic liver disease which include, but not limited to
 - a. Worsening ascites
 - b. Bleeding from esophageal, gastric, or hemorrhoidal varices
 - c. Worsening hypersplenism (hard to differentiate from bone marrow toxicity)
 - d. Hepatic encephalopathy
 - e. Hepatopulmonary syndrome
 - f. Portopulmonary hypertension
3. Extra-hepatic conditions related to alpha-1 antitrypsin deficiency which include, but not limited to
 - a. Chronic obstructive pulmonary disease
 - b. Hypoxia

Data collection procedures for adverse events

Patients will be interviewed regarding medical conditions, medication changes, and symptoms that have occurred at each study visit. An AE form will be completed if any adverse event is reported.

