A Preliminary Study of the Efficacy and Safety of Carbamazepine in Severe Liver Disease Due to Alpha-1 Antitrypsin Deficiency

If a study coordinator or investigator learns of any hospitalizations or other adverse events between study visits, an AE form will be completed. All AEs and SAEs from time of study entry (consent) up to the end of follow-up will be reported to the Sponsor-Investigator. A SAE form will be completed for all adverse events rated as serious. Patients will be followed for all ongoing unresolved adverse events until they are either resolved, or in the opinion of the Sponsor-Investigator or treating sub-investigator, the patient is medically stable.

The Sponsor-Investigator will assess the relationship of each adverse event to the use of study drug, based on available information, using the following as guidelines:

1. Unlikely related: No temporal association, or the cause of the event has been identified; or the drug cannot be implicated.
2. Possible related: Temporal association is present, but other etiologies are likely to be the cause; however, involvement of the drug cannot be excluded.
3. Probably related: Temporal association is present; other etiologies are possible, but unlikely.

Reporting procedures

All SAEs that are unexpected and related to study drug will be reported to the Sponsor-Investigator within 72 hours by telephone. This reporting includes serious adverse events that occur from the time the patient has signed the clinical trial consent. The Sponsor-Investigator will promptly review all SAEs and will notify the reviewing IRB and FDA within requisite time frames if an event is considered to be unexpected and possibly or definitely related to the study drug (e.g., *serious, unexpected adverse events related to the investigational drug to the agency within 15 days of the Sponsor becoming aware of such; deaths and life-threatening reactions reported to the agency within 7 days of the Sponsor's awareness*). The Sponsor-Investigator will notify all sub-investigators of unexpected SAEs related to the CBZ. Status reports on all adverse events will be generated under the direction of the Sponsor-Investigator and sent to the DSMB every month and will include the relationship of the AE to trial medication, the severity of the event and if the event is resolved or ongoing. All AEs will be reported annually to the FDA and reviewing IRB, as required

Statistical considerations

Analysis

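### Listed disease outcomes are exempted from SAE status with no exception for cases that meet the protocol's own seriousness criteria, so SAE counts can be too low

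*Combined protocol and SAP*

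**What the plan says.** All of this is in the combined protocol and SAP.

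- **Adverse events, Definition.** An SAE is "an untoward medical occurrence that results in any of the following: Death, or an event that is either life-threatening", or one that "requires in-patient hospitalization or prolongation of existing hospitalization", or one that causes lasting disability or a birth defect. Important medical events may also qualify on medical judgment.
- **Same subsection, next paragraph.** "A SAE which is unexpected and is drug related (even remotely) will require expedited reporting to the FDA" and to the IRB. The exemption follows directly: "The following events are disease outcomes and will not be considered to be serious adverse events as they can occur in the usual course" of AT deficiency. The list covers hepatocellular carcinoma, complications of chronic liver disease and extra-hepatic AT-deficiency conditions. Among the liver complications are "Bleeding from esophageal, gastric, or hemorrhoidal varices" and "Worsening hypersplenism (hard to differentiate from bone marrow toxicity". The second and third categories are expressly not exhaustive.
- **Data collection procedures for adverse events.** "A SAE form will be completed for all adverse events rated as serious". Ordinary AE forms are completed for every reported event, including hospitalizations that staff learn of between visits.
- **Adverse Events and Toxicity Management.** The drug effects to be watched for include "bone marrow depression as well as for hepatotoxicity that could worsen the liver disease".

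**The concern.** The definition asks what happened to the subject, while the list asks what the diagnosis was. The two give different answers for any listed event that is life-threatening or leads to admission, and no text says which prevails. If the specific list limits the general definition, such events are non-serious by rule.

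This matters because Objective 4 is whether CBZ is safe and tolerated in severe liver disease, and the background section says that no clinical studies of CBZ in known liver disease are available. Serious liver events are therefore a central safety question. The typical eligible subject has cirrhosis with portal hypertension, so the exempted events are ones this population is prone to. The Rationale for Placebo Control relies on the placebo arm for natural-history data on complications of cirrhosis. Comparing the arms is how drug effect would be separated from disease, but the list assigns these events to disease in advance and takes them out of the serious counts.

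**Working it through.** No power, rate or error calculation applies, and the plan gives no figure to reproduce. The check sets the texts side by side.

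**1. Reach of the list.** Named conditions: 1 (hepatocellular carcinoma) + 6 (liver complications a to f) + 2 (extra-hepatic a and b) = 9. Open-ended categories: 2 of 3. Stated exceptions for outcome, severity or relatedness: 0. None appears in the toxicity, dose-alteration, discontinuation, reporting, safety-analysis or DSMB sections either.

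**2. One case under both texts.** Take a treatment-emergent variceal bleed that requires admission and is not fatal.

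| Record | Section | Outcome definition | List |
|---|---|---|---|
| AE form, relatedness assessment | Data collection procedures | yes | yes |
| Monthly DSMB report, annual FDA and IRB report | Reporting procedures | yes | yes |
| Hepatic AE summary (item 4), if classed as hepatic | Safety analysis | yes | yes |
| SAE form | Data collection procedures | yes | no |
| Sponsor-investigator's prompt review of SAEs | Reporting procedures | yes | no |
| All SAEs (item 8) | Safety analysis | yes | no |
| Serious and related AEs (item 9) | Safety analysis | if related | no |
| Biannual DSMB summary | Data and Safety Monitoring Plan | serious stratum | non-serious stratum |

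The last five rows repeat one label. Their number shows where the label is used, not how large the effect is.

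**3. Direction.** Let *n* be the number of unlisted events that meet the outcome definition and *k* the number of listed events that meet it. The SAE count is *n + k* under the definition and *n* under the list. The difference is *k*, which is zero or more. The documents give no event rate, so *k* cannot be estimated.

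**4. Difference between arms.** The loss can occur in both arms (20 CBZ, 10 placebo). If CBZ worsened liver disease, part of the excess would drop out of the serious counts. If it helped, part of the benefit would drop out. The direction of any distortion between arms cannot be derived.

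**5. Deaths.** Death is in the definition and is not itself a listed item. A fatal variceal bleed is therefore an SAE on one reading and exempt on the other.

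**6. Hematologic events.** Only one named item, worsening hypersplenism, is hematologic. The list itself says it is hard to tell from marrow toxicity. Bone marrow depression and hepatotoxicity are not listed, so an event diagnosed as either keeps SAE status if it meets the definition.

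**The case against.** The strongest reply is that a general rule with a specific exemption is a deliberate choice, not a contradiction, and that the protocol gives its reason. That is fair as to intent. But the reason, that these events occur in the usual course of the disease, bears on whether an event is anticipated, not on whether it is serious. Nor is the exemption needed to avoid expedited reports of expected events, because that trigger already requires the event to be unexpected and drug-related. The list follows the expedited-reporting sentence, but its words remove SAE status itself.

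A second reply is that the events are captured elsewhere, and this largely stands. Besides the records in the table, CTCAE grading applies, events that require treatment reduction or discontinuation are recorded, hematologic AEs have their own summary, and AEs are analysed quarterly. A reader might infer that serious liver events go unrecorded or never reach the DSMB or FDA; the documents do not support that. Nor is the tolerability endpoint in the Summary changed, since it refers to adverse events and not to SAEs. Still, the monthly DSMB report names relatedness, severity and resolution as its content. It does not rule out seriousness, but does not promise it. Approach to safety/tolerability promises particular attention to serious CBZ-related events, yet does not restore the label.

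A reader might also infer that expedited reporting is lost. That trigger does start from SAE status, but it concerns only unexpected, drug-related events. The investigators separately commit to IRB policies on serious and unexpected events, and those policies cannot be seen here. The effect on IRB reporting is therefore uncertain.

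**Conclusion.** The point holds for the records that depend on the SAE label: the SAE form, the sponsor-investigator's prompt SAE review, SAE summaries 8 and 9, and the serious stratum of the biannual DSMB summary. Followed as written, the list can only leave SAE counts equal to or below those under the protocol's own definition. It is a stated rule that needs correcting, not a missing detail, and should be fixed.

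This rests on one assumption: that staff apply the specific list over the general definition. The number of subjects affected is unknown. Fatal listed events are ambiguous rather than clearly excluded, and the hematologic part is confined to worsening hypersplenism. A reader might infer that the rule hides harm from CBZ. The documents do not show that; they show mislabelling of listed events that meet the outcome definition, with no derivable direction for the comparison of arms.

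**What to change.** Reconcile the two texts in the Definition subsection:

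- Rate seriousness by the existing outcome definition for every event, including listed ones and including deaths.
- Keep the list only to mark events anticipated in this population.
- State that listing neither settles relatedness nor makes an event expected for the drug. Without this, the list could be used to close the expedited route through expectedness. Relatedness, including for hypersplenism, stays with the assessment already required for each AE.
- Leave the expedited trigger as written.

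Summaries 8 and 9 and the DSMB serious stratum then include these events with no new table. If the DSMB wants a version by arm for its closed session, someone outside the blinded investigative team should prepare it. The Data and Safety Monitoring Plan has the investigators prepare the reports, and the Randomization text names the Study Monitor as the only unblinded team member.

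The cost is protocol wording, some additional SAE forms (number unknown) and possibly a few expedited reports for events that are unexpected and drug-related. No dose, stopping or withdrawal rule changes.

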Hepatic venous pressure gradient (HVPG) measurements have been integrated into routine clinical practice in the assessment of adults with cirrhosis (10, 11) During this procedure transvenous liver biopsies (typically 2 to 4 samples from different segments of the liver) can be obtained thus providing additional clinical and research information from the same procedure. The procedure can be performed with local anesthesia but usually is done with sedation or low levels of general anesthesia (12, 13). In the study by Manolakopoulos, HVPG dropped significantly in 19 subjects after a 12-month course of lamivudine therapy for chronic hepatitis B (14.4 ± 3.9 vs 12.4 ± 3.3 mmHg, $p = 0.007$) (12). In the study by Roberts, of the 10 subjects with chronic hepatitis C with a sustained viral response to pegylated interferon and ribavirin, there was a significant drop in HVPG (9.0 ± 4.0 vs 6.9 ± 3.4 mmHg, $p = .05$) (13). This procedure provides an outstanding global assessment of the degree of fibrosis by assessing overall resistance to portal flow via the calculated portal pressure. The global nature of the measurement avoids problems related to sampling errors from non-homogeneous patterns of fibrosis.

AUTOPHAGY

Because liver damage is caused by intracellular accumulation of the mutant ATZ, the pathways by which this mutant protein is degraded within liver cells have been the subject of a number of investigations. Indeed, one of the major hypotheses about this disease is that pathways for intracellular degradation of mutant ATZ play a role in protecting some deficient individuals from liver disease or in decreasing the severity of the liver disease phenotype (2). The studies in this area have shown that at least 2 major cellular disposal pathways are involved, the proteasome and autophagy (3). Autophagy is a tightly regulated process by which cells consume unwanted cytoplasmic macromolecular constituents and recycle nutrients for cellular remodeling. During autophagy, a double membrane known as the isolation membrane wraps around portions of the cytoplasm to form a double-membrane vesicle, the autophagosome. The engulfed cargo, including organelles and damaged proteins, is degraded upon autophagosome fusion with late endosomes or lysosomes. Autophagy appears to be particularly important for disposal of polymerized and/or aggregated mutant ATZ and the pathway is specifically activated when ATZ accumulates in the endoplasmic reticulum of liver cells (3).

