During therapy, study subjects will be seen on a regular basis to assess their clinical status and to obtain standard biochemical measures of liver and renal function, cell counts, etc. Visits will also include a full history and physical examination. Specific assessments and queries will be made for any signs or symptoms of liver disease. Child-Pugh (CP) score and MELD score will be calculated at each study visit. Other than blood collection during study visits, no additional invasive testing is proposed until the week 52b visit when a repeat liver biopsy and HVPg will be obtained. The procedure for the liver biopsy and HVPg will be identical to the procedure used in the screening visit. Data will be collected from procedures undertaken as part of clinical follow up (e.g. endoscopy reports, imaging studies, etc.).

If the study subject undergoes liver transplantation during the study period, samples will be obtained at the time of surgery to provide follow up data. If a subject dies during the study period and the family consents to an autopsy, samples of liver tissue will be obtained at autopsy to provide follow up data. In these cases, follow up HVPg measurements will not be available.

Potential for suicide attempts will be monitored with the Columbia Suicide Severity Rating Scale (C-SSRS) at study visits the week of enrollment through week 52a. It is a semi-structured, clinician-administered instrument to track severity of both suicidal behavior and ideation. This measure is reliable and valid and has been used in previous clinical trials (44, 45). Patients will be withdrawn from the trial if the C-SSRS identifies suicidal ideation or behavior and then the patient will then be referred for mental health evaluation and treatment.

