Objective 1. Determine whether CBZ treatment reduces hepatic ATZ load in AT-deficient patients with severe liver disease.

The primary analysis will test for differences between the treated and placebo groups in the change from baseline to follow-up in the number of hepatocytes with PAS+/diastase-resistant globules using an unpaired t-test (or nonparametric equivalent if appropriate). Given the small sample size, we do not assume that randomization will balance treated and placebo groups at baseline with respect to outcome variables. Therefore, we will compare changes over the course of the treatment rather than differences at the end of the treatment. Secondary analyses will look at the area of a liver section occupied by these globules and the

A Preliminary Study of the Efficacy and Safety of Carbamazepine in Severe Liver Disease Due to Alpha-1 Antitrypsin Deficiency

steady state level of ATZ by immunoblot again using an unpaired t-test (or nonparametric equivalents if appropriate) of the differences between the treated and placebo groups in changes from baseline to follow-up.

Given that the sample is small, randomization may not balance the groups with respect to important covariates, though our ability to detect statistically significant differences is likewise limited to relatively large effect sizes. Furthermore, the number of variables that could be adjusted for in a regression model is also limited by the sample size, as is our ability to do subgroup analyses. However, as exploratory analyses, we will compare the distributions of important confounders between treated and placebo groups and fit multiple linear regression models that include independent variables, in addition to treatment group and baseline values of outcome measures, with variables whose distributions are markedly imbalanced between treatment groups.

Objective 2. Determine whether CBZ treatment reduces hepatic fibrosis in AT-deficient patients with severe liver disease.

Analysis will proceed as in objective 1; however, the outcome will be hepatic fibrosis. The primary analysis will compare treatment group differences in baseline to follow-up changes in hepatic hydroxyproline concentration using an unpaired t-test (or nonparametric equivalent if appropriate). Secondary outcome measures will include Sirius red staining of the liver. Exploratory analyses using multiple regression models will proceed as described above.

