The only available data come from studies we have carried out in mice. We found statistically significant differences between 18 treated and 11 placebo mice in the number of globule-containing hepatocytes after CBZ treatment. At the end of the study there were an average of 1088 (sd=260) globule-containing hepatocytes among control and 323 (sd=179) globule-containing hepatocytes among treated mice (14). Assuming that the average number of globule-containing hepatocytes at baseline was the same in the two groups of mice, then the group difference at follow-up (765 globule-containing hepatocytes) reflects the group difference in changes. Assuming equal standard deviation (sd) in the two groups, the effect size was 3.5. Then, for the proposed sample size (20 treated:10 controls) and a two-sided type I error of 5% there would be 80% power even if the effect is 1.1, about 1/3 of what was found in mice. This translates to being able to detect a drop in the treated group of 765 globule-containing hepatocytes compared to a drop in the controls of 514 (rather than 0).

For the second objective of fibrosis the only relevant data come from hepatic hydroxyproline concentrations in mice after CBZ treatment. There were statistically significant differences between the treated and placebo groups in hepatic hydroxyproline concentrations after CBZ treatment with values of 2.27 (sd=1.02) in 24 control mice and 1.21 (sd=0.70) in 25 CBZ-treated mice (14). Assuming that the hepatic hydroxyproline concentrations at baseline were the same in the two groups of mice, then the group difference at follow-up (1.06) reflects the group difference in changes. Assuming equal standard deviation (sd) in the two groups, the effect size was 1.2. Then, for the proposed sample size (20 treated:10 controls) and a two-sided type I error of 5% there would be 80% power even if the effect is 1.1, about 1/10 of what was found in mice. This translates to being able to detect a drop in the treated group of 1.06 compared to a drop in the controls of 0.106 (rather than 0).

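### The change-score t-test guards only partly against the baseline imbalance it was chosen for; a fixed baseline-adjusted regression should be primary for Objectives 1 to 3

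*Combined protocol and SAP*

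**What the plan says.** Statistical considerations, Analysis, Objective 1, makes an unpaired t-test (or a nonparametric equivalent) on change from baseline the primary analysis of globule-containing hepatocytes. The reason given is: "Given the small sample size, we do not assume that randomization will balance treated and placebo groups at baseline with respect to outcome variables". The conclusion drawn is: "Therefore, we will compare changes over the course of the treatment rather than differences at the end of the treatment".

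A baseline-adjusted model does appear, but only as exploratory. The plan will "fit multiple linear regression models that include independent variables, in addition to treatment group and baseline values of outcome measures", adding whichever variables turn out to be markedly imbalanced. Objectives 2 (hydroxyproline) and 3 (HVPG) follow the same scheme.

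The Randomization section stratifies by non-selective beta-blocker use. No primary analysis uses that stratum.

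Power calculations states for globules that "there would be 80% power even if the effect is 1.1, about 1/3 of what was found in mice", and translates this into "being able to detect a drop in the treated group of 765 globule-containing hepatocytes compared to a drop in the controls of 514".

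**The concern.** The plan names a problem, chance imbalance in the outcome at baseline, and picks a method that solves it only in a special case. A change score subtracts the whole baseline value. If a subject's follow-up value depends on baseline with a slope below 1, as happens when single measurements are noisy, that over-corrects. The arm that starts higher then appears to fall more, even with no drug effect.

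The plan itself expects noisy measurements: the placebo rationale cites sampling variability in biopsy and HVPG, and the text under Objective 3 cites heterogeneity within the liver. With one small trial, part of the primary result could be regression to the mean, which can mimic a drug effect or hide one. The baseline value needed to remove this is already collected.

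**Working it through.** **Inputs.** 20 treated and 10 placebo, two-sided 5% (Study design; Power calculations). Mouse end-of-study SDs of 260 and 179 (Power calculations). HVPG means and SDs from two antiviral studies (background paragraph on HVPG). The baseline/follow-up correlation ρ for globules and hydroxyproline is not given, so it is an assumption, shown from 0 to 0.9.

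**The plan's own figure.** Root-mean-square SD = √((260² + 179²)/2) = 223.2. With 28 df (noncentral t), an effect of 1.1 SD has 78.3% power, and 80% needs 1.124 SD. 1.124 × 223.2 = 251 cells, and 765 − 251 = 514. The plan's figure reproduces. It uses the end-of-study SD as the SD of change.

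**How often the arms differ.** The baseline gap D has standard error √(1/20 + 1/10) = 0.387 SD. P(gap above 0.5 SD) = 2 × (1 − Φ(0.5/0.387)) = 19.7%. At 16:8 the standard error is √(1/16 + 1/8) = 0.433 SD, giving 24.8%.

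**What remains under no effect.** Expected difference in change = (slope − 1) × D. Follow-up only: slope × D. Baseline-adjusted regression: 0. With equal SDs, slope = ρ.

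**Null rejection rates (%)**, simulated with normal data, 20:10, equal SDs, 400,000 randomizations per ρ. Repeat runs differ by a few tenths. The last column takes 223.2 as the SD, so D = 0.5 SD is 112 cells.

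| ρ (assumed) | Change, gap > 0.5 SD | Change, gap ≤ 0.5 SD | Follow-up only, gap > 0.5 SD | Adjusted, gap > 0.5 SD | Spurious cells at D = 0.5 SD (share of 251) |
|---|---|---|---|---|---|
| 0 | 16.4 | 2.2 | 5.0 | 5.0 | 112 (44%) |
| 0.3 | 13.3 | 3.0 | 7.1 | 4.9 | 78 (31%) |
| 0.5 | 10.9 | 3.6 | 10.9 | 4.9 | 56 (22%) |
| 0.7 | 8.7 | 4.2 | 16.4 | 4.8 | 33 (13%) |
| 0.9 | 6.1 | 4.7 | 23.4 | 5.0 | 11 (4%) |

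Over all randomizations the change-score test rejects 4.9 to 5.1%.

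**HVPG.** The background reports that "HVPG dropped significantly in 19 subjects after a 12-month course of lamivudine therapy for chronic hepatitis B" (14.4 ± 3.9 to 12.4 ± 3.3 mm Hg, p = 0.007). If that p-value is from a paired t-test:
- t on 18 df = 3.04, so SD of change = 2.0 × √19/3.04 = 2.86
- ρ = (3.9² + 3.3² − 2.86²)/(2 × 3.9 × 3.3) = 0.695
- slope = 0.695 × 3.3/3.9 = 0.59, with a 95% interval of about 0.28 to 0.90

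The hepatitis C study (n = 10, 9.0 ± 4.0 to 6.9 ± 3.4, p = .05) gives ρ = 0.696 and slope 0.59, interval about 0.09 to 1.09.

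If the fall in SD also occurs without a drug effect, the change score rejects 12.6% at 20:10 and about 11% at 16:8 when the gap exceeds 0.5 SD. If SDs stay equal at the same ρ, it rejects about 8.5 to 9% and 8%. At D = 0.5 × 3.9 mm Hg the spurious difference is 0.41 × 1.95 = 0.80 mm Hg in the first case and 0.305 × 1.95 = 0.59 mm Hg in the second. The plan's detectable drop is 3.4 mm Hg.

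**Unequal SDs.** With follow-up SDs as in the mice (260 control, 179 treated), no effect and ρ from 0 to 0.7, overall rejection is:
- pooled change t-test: 6.4 to 6.6%
- Welch change t-test: 5.0 to 5.2%
- adjusted regression, ordinary errors: about 8%
- adjusted regression, HC3: about 4.5%

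At ρ = 0.7 with a gap above 0.5 SD, ordinary-error adjustment rejects 8.6% against 9.6% for change, so most of its advantage is lost. HC3 stays between 4.2 and 5.1% across the equal-SD and mouse-SD settings up to ρ = 0.7. At ρ = 0.9 with the mouse SDs (200,000 further runs) the arms' slopes differ noticeably, and HC3 rejects about 5.8% against 6.5% for change in the gap randomizations.

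**The case against.** The strongest defence has four parts.

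- **The test is valid.** A reader might infer from the conditional rates that the primary analysis inflates type I error. It does not: the excess in imbalanced randomizations is offset by rates below 5% in the rest. This stands in full. The point concerns what happens once the arms are seen to differ, which is the case the plan says it wants covered.
- **Change beats the alternative that the plan rejects.** With equal SDs and ρ above 0.5 it is better than comparing follow-up values, and it removes about 70% of an imbalance at ρ = 0.7 and 90% at 0.9. It would therefore be wrong to say that it gives no protection. At ρ = 0.5, the value that the 251-cell figure implies if SDs are equal, it does no better than follow-up alone.
- **An adjusted model is already planned.** It is, but a reader who concludes that this exploratory model should simply be promoted goes too far. Its extra covariates are picked after imbalance is seen, so it is not a fixed primary analysis.
- **The HVPG slope is weak evidence.** The data come from treated patients, the background names no test, and the second interval includes 1. They show that a slope below 1 is plausible; they do not establish 0.59.

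A further inference to resist is that the 251-cell figure shows an underpowered trial. It is a minimum detectable effect, about a third of the mouse effect. At half the mouse effect (765/2, about 382 cells) change-score power is 85% even at ρ = 0 with equal SDs.

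**Conclusion.** The concern holds as one of conditional bias. The change score protects only partly against baseline imbalance. In about one 20:10 randomization in five the null rejection rate is raised to somewhere between 6 and 16%, depending on a correlation that the documents do not give for the two tissue outcomes; for HVPG the range is about 8 to 13%. Adjusting for baseline brings it to about 5%.

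This rests on roughly normal data, a linear relation with baseline and, for the main table, equal SDs. If ρ is near 0.9 the practical gain is small. The case does not rest on power, and it does not make the planned test invalid. It is a change that should be made, not a fatal flaw.

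**What to change.** For Objectives 1 to 3, prespecify as primary: linear regression of the follow-up value on treatment group, baseline value and the beta-blocker randomization stratum, with no covariates chosen after imbalance is seen, HC3 standard errors, and the adjusted treatment difference with its 95% CI. Keep the change-score comparison (Welch) and the nonparametric comparison as sensitivity analyses. Ordinary standard errors should not be used without a check, given the rejection rate of about 8% with the mouse SDs.

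**Cost.** SAP wording only; no new data. Residual degrees of freedom fall from 28 to 27 with baseline, or 26 with the stratum; the stratum costs at most about 0.3 points of power. HC3 costs about 2 to 5 points relative to ordinary errors when SDs are equal. With change-score power held at 80% and equal SDs, ordinary-error adjustment gives 84% at ρ = 0.7, 80% at 0.9 and 79% at 0.95. With HC3 there is thus a net loss of a few points at very high ρ.

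**Optional.** Add to Power calculations that the 251-cell figure takes the end-of-study SD as the SD of change. With equal baseline and follow-up SDs, the SD of change is SD × √(2(1 − ρ)), so this means ρ of about 0.5. At ρ = 0.3 change-score power for 251 cells is about 66%.
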